PLWH can be powerful change agents for HIV prevention within communities. Our research suggests that as PLWH receive ART and restore their health, they are motivated to protect their social network members and engage in prevention advocacy (i.e., encourage friends and family to seek HIV testing and care and reduce HIV risk); however, the quality of this advocacy is hampered by challenges related to message content, style and timing of delivery, and the selection of appropriate recipients for advocacy. With effective advocacy training, mobilizing PLWH to be change agents within their networks has the potential to be a “game changer” for HIV prevention, particularly in high-prevalence settings where virtually every family is touched by HIV. In the proposed research, we will conduct a randomized controlled trial (RCT) of *Game Changers*, an 8-session peer-led group intervention that aims to empower and mobilize PLWH to be agents for HIV prevention in their social networks. By decreasing stigma among PLWH and their social network members, as well as training PLWH on key strategies to engage social network members in discussions around HIV, *Game Changers* provides PLWH with the tools to do prevention advocacy and is facilitated by peers who are from participants’ communities and living with HIV. *Game Changers* was developed through an NIMH-funded R34 in partnership with the Infectious Diseases Institute (IDI), a public-private partnership in Kampala that provides care to PLWH, that trains healthcare workers on HIV care and treatment, and conducts research to address the HIV epidemic. As part of the intervention development process, the team conducted focus groups with PLWH and social network members, and engaged with community stakeholders, including a community advisory board. Our pilot RCT with 98 PLWH and 57 social network members revealed promising preliminary intervention effects on reduced internalized stigma and increased HIV-serostatus disclosure to social network members among PLWH, as well as increased condom use and HIV testing among social network members.

The **Specific Aims** are:

1. To conduct a fully powered RCT of *Game Changers* to test intervention effects on the primary outcomes of increased HIV testing, reduced condomless sex, and decreased enacted HIV stigma among social network members of participating PLWH.

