The intervention showed preliminary effects consistent with hypotheses. Among alters at month 5, condomless sex with main partners in the past month decreased by 7.7% (46.2% to 38.5%) in the intervention group vs. an increase of 10.5% (57.9% to 68.4%) in the control group; this was a large effect (Cohen's $d = .76$), despite marginal statistical significance in this underpowered small pilot [OR (95% CI)= 0.3 (.1-1.2), $p=.08$]. Among the 20 alters who were HIV-negative prior to the 5-month follow-up and who were not tested for HIV between baseline and the 5-month follow-up, 5 of 15 intervention alters (33.3%) vs. 1 of 5 control alters (20.0%) reported being tested for HIV post-intervention (in between 5- and 8-month follow-ups), which represents a small-to-medium effect size (Cohen's $d = .30$). In terms of mediators, alters of intervention participants were significantly more likely to report engaging in prevention advocacy discussions (mainly on HIV testing, condom use, and ART) in their social networks ($p=.04$). Note that, because we only interviewed a small number of alters for feasibility rather than to detect effects, we did not interview all alters with whom the PLWH did prevention advocacy, and PLWH did not do prevention advocacy with all alters interviewed. Thus, we would expect effects to be stronger in the proposed study, in which we will recruit a larger number of alters.

Results for PLWH also showed effects consistent with hypotheses. Compared to controls at baseline vs. follow-up, intervention participants were more likely to report engaging in prevention advocacy [b (SE) = 0.4 (0.2), $p = .017$], especially related to HIV testing, condom use, and number of partners (all $p < .05$). Intervention participants were less likely to feel internalized [b (SE) = -0.3 (0.1), $p = .012$] and anticipated HIV stigma [b (SE) = -0.5 (0.2), $p = .011$], and to have concerns about disclosure [b (SE) = -0.3 (0.1), $p = .028$], and were ten times more likely to have disclosed to a main partner [OR (95% CI) = 10.0 (1.5-67.7), $p = .022$], compared to control participants. Moreover, intervention participants were more likely to report that all of their alters had been tested ($p < .10$), and that they disclosed to a greater proportion of alters ($p=.05$). The intervention also had effects on social network structure: intervention participants' networks became denser over time, with more and stronger connections among alters [b (SE) = 0.1 (0.3), $p = .004$].

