Assessment: Overview. Under the leadership of [name] (MPI), the assessment was developed to include individual-level survey questions for PLWH and alters, and a social network assessment for PLWH only. The 60-75 min. assessment for PLWH and 20-minute assessment for alters will be administered at baseline and months 6, 12, and 18. The 6-month interim period is consistent with the Ugandan Ministry of Health recommendation for repeated HIV testing every 6 months (one of our primary outcomes), and the 18-month follow-up period will allow us to better assess durability of effects. Participants will receive 30,000 Ush (~\$8) per assessment, and 30,000 Ush (~\$8) transportation reimbursement for each intervention session. We will collect tracking information (phone numbers, mapped addresses, contacts for family/friends with whom they have frequent contact). Clinic staff, including “Linkage Facilitators” (i.e., expert patients identified by IDI clinic staff who track patients) will help to track patients that we have difficulty reaching (if participants consent). In our other 12-month longitudinal studies of PLWH in Uganda, we have achieved $\geq 90\%$ retention, and retention in our R34 pilot was $> 95\%$ for both PLWH and alters at the final month-8 follow-up. Assessments will be administered on laptops using Egoweb,¹⁰¹ social network and survey data collection and analysis software developed at RAND. The assessments include the following sections, which we have refined across multiple studies in the US and Uganda (and translated into Luganda; alphas below provided from Ugandan studies).

Individual-Level Outcomes. Sexual Behavior (condomless intercourse) in the past 6 months will be assessed with standard items on number of partners; number of times engaged in intercourse (vaginal or anal) and of those, number of times a condom was used; and perceived HIV serostatus of partner(s).

Alters' HIV Testing (among alters of negative or unknown serostatus) will be assessed. At every time-point, alters will report whether they have been tested for HIV and if so, the date of their most recent test and result,¹⁰⁰ and whether they intend to get tested in the next 6 months (1, not at all, to 5, very much) or start HIV care and ART (if warranted). Self-reported HIV testing and status has been found to be reliable.¹⁰¹⁻¹⁰⁴

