Network Composition: Using PLWH's reports, we will assess alters' demographics; relationship (e.g., family, friend, partner) and closeness to ego (PLWH); interaction frequency; and usual mode of interaction (e.g., in-person, text). For each alter, we will ask the PLWH if they have disclosed his/her serostatus to the alter, and if the PLWH knows the alter's serostatus and testing status. If the participant thinks the alter is HIV-positive, we will ask whether the participant thinks the alter is in care and on ART. To assess prevention advocacy, we will ask participants if they have encouraged each alter regarding HIV protective behaviors (e.g., HIV testing, PrEP, condom use, ART use if positive). By assessing alter characteristics, we can measure the context of prevention advocacy, i.e., characteristics and network position of individuals who are prevention advocacy recipients. To assess enacted stigma among alters, participants will be asked whether they have heard each alter express stigmatizing beliefs (ever and since last assessment), as we have done previously,¹²⁰ whether they have avoided the alter because they believe he/she would mistreat them (anticipated stigma) and whether the alter has rejected them (enacted stigma). We will derive network composition indicators (% of different types of alters; e.g., men/women, disclosed to, tested).

At each follow-up, we will use Egoweb's longitudinal features developed in our prior research to update network information. Participants will be asked the network elicitation questions, and then shown a list of alters from the prior assessment, allowing them to match alters named at follow-up against those previously included. The few personal social network studies that have measured networks longitudinally suggests that networks can change substantially in a short time.^{121, 122} These methods allow us to examine whether the intervention is associated with network change, e.g., greater density, as in the pilot.

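### The primary enacted-stigma outcome is described only on a list of alters that each PLWH draws up again after randomisation, with no stated denominator and no described follow-up of alters left off the list

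*Combined protocol and SAP*

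**What the plan says.** Aim 1 (Specific Aims) names "decreased enacted HIV stigma among social network members of participating PLWH" as one of three primary outcomes.

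The measure sits in "a social network assessment for PLWH only" (Assessment: Overview). Under Network Composition, "participants will be asked whether they have heard each alter express stigmatizing beliefs", both ever and since the previous assessment. A further item, whether the alter has rejected the PLWH, also carries the enacted-stigma label. No alter self-report of stigma is described.

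Under Social Network (PLWH only), the list holds 20 people with whom the PLWH has communicated in the past 6 months. Under Randomization, the envelope is opened after the baseline survey, so every later list is post-randomisation. At each follow-up, "Participants will be asked the network elicitation questions, and then shown a list of alters from the prior assessment", and the stated purpose of showing the list is to match names. The same paragraph notes that "networks can change substantially in a short time" and treats network change as something the intervention may cause.

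The plan derives percentages of types of alter in the network but gives no denominator or analysis set for stigma. Statistical Analysis (Aims 1-3) weights for participants who drop out and imputes item nonresponse. It says nothing about alters who leave a list.

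**The concern.** Aim 1 reads most naturally as a change in how network members behave. The measure described can also move because the people being rated are different people.

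Two features make that plausible. First, listing requires recent contact, and the outcome includes rejection by the alter. Rejection or avoidance can end contact, so the event being measured can remove the alter from the list that would record it. Second, on the 'ever' item, an alter who stays listed and is reported consistently cannot go from yes to no, so a fall on that item can come only from turnover.

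The other two primary outcomes, HIV testing and condomless sex, come from enrolled alters who are drawn from the baseline list and then followed. Stigma has no such fixed set. If stigma reports on dropped alters are not collected at the visit, they cannot be recovered at analysis.

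**Working it through.** **Inputs from the documents.** 20 alters per list; re-listing at months 6, 12 and 18. There is no plan figure for stigma to reproduce: Statistical Power covers condomless sex only for alters, and no stigma prevalence or turnover rate by arm is given.

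**Assumed inputs.** 15% of alters stigmatise at baseline (3 of 20, leaving 17 others). No alter changes. Both arms lose 25% of the 17 others (4.25). Controls lose 25% of stigmatising alters; the intervention arm loses 35% or 50%. Lists are refilled to 20.

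**Formula.** Follow-up share = [3 × (1 − loss) + new alters × stigma rate among new] / 20, where new alters = 3 × loss + 4.25.

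*Replacements at 15%*
- Control, 25%: (2.25 + 5.00 × 0.15) / 20 = 3.000 / 20 = 15.0%
- Intervention, 35%: (1.95 + 5.30 × 0.15) / 20 = 2.745 / 20 = 13.7%
- Intervention, 50%: (1.50 + 5.75 × 0.15) / 20 = 2.3625 / 20 = 11.8%
- Spurious gap: 1.3 to 3.2 points

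*Replacements at 7.5% in both arms*
- Control, 25%: (2.25 + 5.00 × 0.075) / 20 = 2.625 / 20 = 13.1%
- Intervention, 35%: (1.95 + 5.30 × 0.075) / 20 = 2.3475 / 20 = 11.7%
- Intervention, 50%: (1.50 + 5.75 × 0.075) / 20 = 1.93125 / 20 = 9.7%
- Spurious gap: 1.4 to 3.5 points

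**Direction.** Exchange the loss rates between arms and the same gaps appear with the opposite sign.

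**Equal dropping.** With the same loss rates in both arms the gap is zero. A simulation of re-listed networks (25% background turnover, 89 PLWH per arm after 15% attrition, no alter changing) agrees: about 0 points, with 4.5% to 5.5% of tests rejecting at the 5% level. With 25 extra points of dropping in the intervention arm and 10% to 30% stigmatising at baseline, it gives false falls of 1.9 to 5.0 points.

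**Does matching cure it?** Among matched alters only, the follow-up share is 2.25 / 15.00 = 15.0% in controls and 1.95 / 14.70 = 13.3% to 1.50 / 14.25 = 10.5% in the intervention arm. Against a baseline on all 20 alters the artefact remains. If baseline is also cut to matched alters it disappears in this scenario, but the comparison is then confined to alters selected after randomisation, and one who starts to stigmatise and is dropped is never counted.

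**Does a baseline roster cure it?** Yes, if every baseline alter's status is known: change is exactly zero in both arms. If dropped alters are out of contact and score 'no' on the since-last-assessment item, controls show 2.25 / 20 = 11.3% and the intervention arm 1.95 / 20 = 9.8% to 1.50 / 20 = 7.5%. That is a gap of 1.5 to 3.8 points, no smaller than before. The roster therefore needs a contact rule.

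**The case against.** **The current network is a legitimate outcome.** PLWH are the randomised unit, and the share of stigmatising alters in each PLWH's current network can be compared by arm under intention to treat. If that is the estimand, turnover is part of the effect. This stands, so a reader should not infer that the randomised comparison is broken. The problem arises if the target is change among the same network members, which Aim 1's wording favours but does not settle. The plan should say which it means.

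**The instrument is not shown.** The software might prompt for unmatched alters. That is possible; what can be said is that no such step is described.

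**Differential dropping is not demonstrated.** A reader might infer from the pilot, where intervention "networks became denser over time", that the intervention makes PLWH shed stigmatising contacts. The documents do not support this. Density can rise among the same 20 people, and the pilot section reports no turnover by arm. The sessions teach whom to approach, not whom to drop, and the plan states that the mapping exercise is separate from the evaluation module. Nor is the direction fixed: wider disclosure could bring in alters who react badly and hide a true benefit.

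**A baseline roster does not by itself remove the artefact.** This also stands, as the working shows, and the fix provides for it.

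**Conclusion.** The point holds in a conditional form. A primary outcome is described only on a list re-elicited after randomisation and restricted by recent contact, with no stated denominator and no described stigma data on alters left off. If stigmatising alters are dropped at different rates by arm, the outcome can shift either way with no alter changing; if not, there is no bias.

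The illustrative gap of about 1.3 to 3.5 points rests wholly on assumed prevalence, turnover and replacement rates. It shows the mechanism's scale and does not estimate bias in this trial. It would be wrong to read it as evidence that a fall in stigma here must be an artefact.

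The change should be made because it is cheap and the missing reports cannot be collected afterwards. Confidence is medium, since the instrument and any differential turnover are not visible in the documents.

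**What to change.** 1. At months 6, 12 and 18, load the baseline roster, not only the prior-visit list, and ask the stigma items about every baseline alter whether or not named again. At minimum, do this for every enrolled alter. Record whether there was contact since the last assessment.
2. Define the primary stigma outcome on the baseline roster, stating the item or items and the denominator. Pre-state a rule and a sensitivity analysis for alters with no contact, so that lost contact is not simply counted as no stigma.
3. Report alter turnover by arm and by baseline stigma.
4. Keep the re-elicited network for the network-composition and network-change analyses.

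**Cost.** A few extra items per un-named alter. If 25% are lost per interval and none are named again, the number is 20 × (1 − 0.75) = 5 at month 6, 20 × (1 − 0.75²) = 8.75 (about 9) at month 12, and 20 × (1 − 0.75³) = 11.6 (about 12) at month 18. The burden therefore grows over visits. Because the plan shows only the prior assessment's list, carrying the baseline roster forward may need a change to the Egoweb set-up.

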
Randomized Controlled Trial of *Game Changers*

Overview. The proposed design is an individually randomized group-treatment trial using a clustered design.⁹⁶ We will recruit 210 PLWH and randomize 105 to the intervention and 105 to a no-intervention control arm. Each PLWH will be asked to recruit social network members (alters to whom they have disclosed) (736 total, 368/arm). All participants will complete assessments at baseline, and 6, 12 and 18 months post-baseline to assess improved HIV prevention behaviors within the network, mediators of improved behaviors, and HIV outcomes. Participants will be divided into 7 cohorts of 30 (within each cohort, 15 intervention and 15 control). Intervention implementation for the 7 cohorts will be staggered, such that two will be conducted at a time (i.e., 60 PLWH and 210 alters for two cohorts at a time), except the last wave in which there will be one cohort of 30. [name] will oversee the implementation of the intervention program, while [name] will oversee the assessment, data collection and analysis components of the trial.

Randomization. A blocked 1:1 randomization design with stratification by gender (with randomly alternating blocks of 2, 4, and 6 to prevent anticipation of condition) will ensure balance across arms. All groups will be mixed sex (with approximately equal numbers of men and women/group), and a male and a female facilitator will conduct each group. The statistician will use a random number generator to devise a randomization log and a set of sealed numbered randomization envelopes (to prevent condition foreknowledge). After completing the baseline survey, the interviewer will open the corresponding envelope and record the condition. Although individual randomization entails contamination risk, this type of group intervention—where recipients attend several sessions that use structured content and group interaction to target multiple aspects including internalized stigma, comfort and skills with disclosure, and how and who to engage in advocacy with—is less conducive to contamination. Statistical models suggest $\geq 30\%$ of the control arm must receive the equivalent of a full-strength intervention to result in meaningful contamination,⁹⁷ so with a

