Aims 1-3. Primary analyses will use a standard intent-to-treat approach, applying generalized mixed models (linear for continuous outcomes; logistic for binary outcomes) to the repeated-measures data to examine how intervention effects change over time, using an indicator for study arm, timepoint (baseline vs. follow-up), and timepoint by arm interaction to indicate whether change differs between arms. Our statistical methods will be consistent with advances in the analysis of personal network research,^{66, 135-137} accounting for any correlation among participants in the same intervention group sessions, and among alters referred by the same PLWH (ego), by adjusting standard errors for statistical inference tests with a sandwich estimator as implemented in SAS v 9.4.^{96, 138-141} We will use imputation for item nonresponse and account for non-random dropouts using logistic regressions that assign weights to retained participants that are inversely proportionate to the predicted probability of the participant being retained; if dropout is random, analyses will incorporate design effects. In follow-up analyses, we will explore interactions between each potential moderator and arm, including sex (of ego and/or alter, and concordance between the two) to examine if these variables moderate the intervention effects. If interactions with categorical moderators are significant, we will conduct post-hoc simple main effects t-tests with Bonferroni corrections. For continuous moderators,¹⁴² we will graph significant interactions at low and high levels of each score (± 1 SD). We will conduct post-hoc simple main effects t-tests with Bonferroni correction by comparing differences between discrete points on the regression lines. If *Game Changers* shows significant effects on hypothesized mediators (Aim 3), to test mediation we will compare: (a) Aim 1 models, adding baseline measures of mediator(s); and (b) the same models as in (a), adding post-intervention measures of mediator(s).¹⁴³ We will examine whether including post-intervention mediator(s) in (b)

decreases the coefficient for intervention effects on outcomes relative to the corresponding coefficient from (a). We will use a bootstrapping approach to test whether mediators account for effects.^{144, 145}

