Statistical Power. We calculated power for alter reports of condomless sex at month 18. Based on the pilot, we assume 65% of control alters will report condomless sex at month 18. Starting with 736 alters, and assuming ~15% attrition by month 18 (which is conservative, based on 98% alter retention over 8 months in the pilot, and <10% attrition over 12 months in our other studies in Uganda), we will have 625 alters; accounting for within-ego clustering gives us an effective sample size of 612 for ICC=.01 or 568 for ICC=.05. For ICC=.01, we will have .80 power to detect a group difference of 10.3% (i.e., an intervention rate of 54.7%), and for ICC=.05, we will have power to detect a 10.7% group difference. These differences represent small effect sizes (Cohen's $d = .23\text{--}.24$). For PLWH index participants, using pilot data, we estimate the ICCs of our secondary outcomes to be small-to-moderate (0-.16), and assume 15% attribution and 7 intervention groups (either Game Changers or attention control), with an average cluster size of 12.9 (90 intervention participants/7 groups).^{96, 140, 141} After accounting for within-group correlations, we will have 80% power to detect medium to large differences (.41-.58 SD, based on the outcome) between the study arms at follow-up.

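### The primary test is an arm-by-time interaction with the follow-up visits left undefined, while the power is for a month-18 difference; no primary contrast is named

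*Combined protocol and SAP*

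**What the plan says.** **Outcomes.** The Specific Aims name three "primary outcomes of increased HIV testing, reduced condomless sex, and decreased enacted HIV stigma among social network members of participating PLWH". No visit is attached to any of them. Assessments are at baseline and months 6, 12 and 18.

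**Test.** Statistical Analysis, Aims 1-3, specifies generalized mixed models (logistic for binary outcomes). It describes the terms as follows: "using an indicator for study arm, timepoint (baseline vs. follow-up), and timepoint by arm interaction to indicate whether change differs between arms". Arm, timepoint and their interaction are the only fixed terms listed. The purpose given for the model is to use the "repeated-measures data to examine how intervention effects change over time".

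**Power.** The Statistical Power paragraph begins: "We calculated power for alter reports of condomless sex at month 18". It assumes 65% in controls, an effective sample size of 612 (ICC .01) or 568 (ICC .05), and .80 power for a difference of 10.3 or 10.7 points. It uses no baseline rate, no correlation between visits and no interaction. For index participants it refers only to differences at follow-up, without naming the visit.

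**Role of month 18.** Assessment: Overview says that "the 18-month follow-up period will allow us to better assess durability of effects". It does not make month 18 the deciding visit.

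**Model terms mentioned elsewhere.** Randomization stratifies by gender and also promises to control for contact between control participants and intervention peers, without saying in which model. Sex appears among the potential covariates and moderators.

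**The concern.** The two-level time term and its stated purpose do not fit together: one baseline-versus-follow-up contrast cannot show an effect changing across three follow-ups. There are two readings, and they fail differently.

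- **Pooled.** There is one contrast, the average change over months 6, 12 and 18. It is fixed in advance, but it is not the month-18 difference that was powered and it says nothing about durability.
- **By visit.** There are three contrasts per outcome, and no rule says which one decides.

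Under either reading, the quantity that carries the primary conclusion is not tied to the power statement. If the effect grows or wanes, the pooled and month-18 results can lead to different conclusions from the same data.

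Two model terms are also unsettled. The randomisation stratum is missing from the listed terms. The contamination variable arises after randomisation and is defined only in controls, so conditioning on it in the primary model would undercut the intent-to-treat comparison.

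**Working it through.** **Step 1. What was powered.** The effective sample sizes reproduce with m = 3.5 × .85 = 2.975 alters retained per index participant:

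- 625/(1 + 1.975 × .01) = 612.9 (plan: 612)
- 625/(1 + 1.975 × .05) = 568.8 (plan: 568)

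A two-sided .05 two-proportion test (alpha is assumed, since the plan does not state it) at 65% vs 54.7% with N 612 gives power .74, not .80. The stated 10.3 and 10.7 points are recovered only as increases from 65% (power .797 and .799). That discrepancy is a separate error in the power paragraph and is not caused by the choice of contrast. What matters here is that the plan's figures match a single-visit comparison of two proportions, not an interaction.

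**Step 2. Variance of each contrast.** With 306 effective alters per arm, the month-18 difference has variance

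v = (.65 × .35 + .547 × .453)/306 = .001553, so SE = .0394.

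Assume equal variance at all visits, a common correlation r and the same effective N throughout. The multipliers of v are:

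- month-18 difference: 1
- month-18 change: 1 + 1 − 2r = 2(1 − r)
- pooled change: (1 + 2r)/3 + 1 − 2r = (4/3)(1 − r)
- month-18 difference adjusted for baseline: 1 − r²

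**Step 3. Power** = Φ(d/√(multiplier × v) − 1.96), with d = .103:

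| Contrast | r = .2 | r = .5 | r = .7 |
|---|---|---|---|
| Month-18 difference | .74 | .74 | .74 |
| Month-18 change | .54 | .74 | .92 |
| Pooled change, constant effect | .72 | .89 | .99 |
| Month-18 difference, baseline-adjusted | .76 | .85 | .96 |

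Break-even with the month-18 difference: 2(1 − r) = 1 gives r = .5; (4/3)(1 − r) = 1 gives r = .25. With 284 per arm and 10.7 points (ICC .05), the first three rows are the same to two decimals.

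**Step 4. Effects that are not constant.** These are two assumed patterns, in points at months 6, 12 and 18:

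- Build-up 3.4, 6.9, 10.3: the pooled contrast estimates 10.3 × 2/3 = 6.9, against 10.3 at month 18. Pooled power is .39/.57/.79; month-18 difference .74.
- Fade 10.3, 6.9, 3.4: the pooled contrast again estimates 6.9, against 3.4 at month 18. Pooled power is again .39/.57/.79; month-18 difference .14.

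**Step 5. Scale check.** The plan uses logistic models. Simulated correlated binary data (baseline 65%, 4,000 runs per cell), analysed with a marginal logistic interaction and sandwich standard errors, gave .53/.75/.90 for the month-18 change and .69/.89/.98 for the pooled change. This is a marginal model, not the mixed model that the plan names.

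**Step 6. Which baselines precede allocation.** Randomization says: "After completing the baseline survey, the interviewer will open the corresponding envelope and record the condition". That is the index participant's survey. Alters are contacted from the end of that interview and interviewed over a two-month period, so an alter's baseline may follow allocation. Enacted stigma is different, because the index participant reports it: "To assess enacted stigma among alters, participants will be asked whether they have heard each alter express stigmatizing beliefs". Its baseline precedes the envelope. However, the item asks about ever and about the time since the last assessment, and no earlier assessment exists at baseline. Networks are also re-elicited, so an alter first named at follow-up has no baseline value.

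**The case against.** The form of the test is stated: an arm-by-time interaction. The parenthesis may be shorthand for each follow-up against baseline, which fits the stated purpose better than pooling. If follow-up means month 18 and the arms have equal expected baselines, the change and the difference have the same expected value on the risk-difference scale and differ only in variance. Powering on the final visit is then a common simplification, and a conservative one when r exceeds .5 (for the pooled change with a constant effect, when r exceeds .25). The values of r and the effect patterns are assumed. The month-18 effective N is carried to other visits and to change scores. Only one of three primary outcomes is quantified.

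Most of this stands, and it rules out two stronger readings. A reader might infer that the trial loses power through the mismatch; the documents do not show that, because they give neither r nor the course of the effect. A reader might also infer that the contamination variable is meant for the primary model; the Aims 1-3 text does not list it there, so this only needs a clarifying sentence.

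The objection does not supply a deciding visit. Nor are equal alter baselines assured by the design, since some may be measured after allocation; any change contrast would use them.

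**Conclusion.** The point holds as a gap in pre-specification. The follow-up coding and the deciding contrast are not stated, and the power statement describes a different quantity from the test. Depending on the contrast chosen, power for the same 10.3-point effect runs from .54 to .99 over the assumed range of r, with .74 for the quantity the plan actually powered. With a building or fading effect, the pooled contrast would estimate 6.9 points where the month-18 difference is 10.3 or 3.4.

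These figures are illustrative. They apply to condomless sex only and rest on two-sided .05, a common r, a normal approximation on the risk-difference scale and effective N 612 at every visit. They show that the choice matters, not that the trial is underpowered. An open choice among visits exists only if time is coded by visit; under the pooled reading the contrast is fixed but does not match the powered one. The effects of adjusting for gender or contamination cannot be sized from the documents.

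**What to change.** 1. **Contrast.** Code time by visit (baseline, 6, 12, 18). For each primary outcome, name the month-18 between-arm difference as primary, to match the power paragraph. Make months 6 and 12 and the average over visits secondary.
2. **Baseline.** Enter the baseline outcome as a covariate, and not also as a response level, only where it was measured before the envelope was opened. Where an alter's baseline may follow allocation, use the month-18 difference without it. For enacted stigma, use a baseline item with a comparable recall period, and say how alters first named at follow-up, who have no baseline value, are handled.
3. **Power.** Restate it for this contrast, with alpha and any assumed r.
4. **Stratum.** Add the index participant's gender to the primary model.
5. **Contamination.** State that the variable is excluded from the primary intent-to-treat model and is reported descriptively or in a sensitivity analysis.

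The cost is mostly SAP wording and one recalculated paragraph, plus a check of each baseline date against the envelope date wherever alter baselines are to be used, and a check of the baseline stigma item. The downside is that the result is tied to one visit, the restated power may be less favourable, and a month-18 contrast has little power if the effect fades (.14 in the fade example).
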